6.1.4 Adjustments for Covariates

Baseline lesion count will be a covariate for the efficacy endpoints for acne lesion counts. No other covariates are planned to be used in the analyses for this study.

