Descriptive statistics (including mean, median, standard deviation [SD], minimum, and maximum, unless otherwise stated) will be presented for the following parameters by study group using both the ITT and PP analysis sets:

- Inflammatory, non-inflammatory, and total lesion counts at Baseline, Day 14, Day 28, Day 56, and Day 84,
- Absolute and percent change from Baseline in inflammatory, non-inflammatory, and total lesion counts at study Day 14, Day 28, Day 56, and Day 84,
- IGA scores and frequency and percent distribution of the dichotomized IGA at study Day 14, Day 28, Day 56, and Day 84.

This Phase 2 study is designed to identify the response to two different dosing frequencies and two concentrations of BTX 1503. Statistical tests applied to the outcomes will be exploratory. No adjustments for Type 1 error will occur.

[figure not shown]
The change from Baseline in lesion counts (inflammatory and non-inflammatory; separate and combined, and total) at Days 14, 28, 56, and 84 will be analyzed using ANCOVA with Baseline lesion count and treatment as covariates. Success on IGA defined as a score of clear or almost clear and/or at least a 2-grade improvement from Baseline at Day 14, Day 28, Day 56, and Day 84 will be analyzed using logistic regression, adjusting for Baseline IGA.

Safety Analyses:

All subjects who receive at least one confirmed dose of study drug and have at least one post-Baseline assessment will be included in the safety analyses. Safety analyses will include summaries of treatment-emergent adverse events (TEAEs), serious AEs (SAEs), and changes in laboratory assessments. TEAEs and SAEs will be summarized by treatment group, the number of subjects reporting events, system organ class, preferred term, severity, relationship to study drug, and

| | |

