5. STUDY ENROLLMENT AND WITHDRAWAL

5.1. Inclusion Criteria

To be included in the study, subjects with acne vulgaris must meet the following inclusion criteria.

1. Subject (or legal guardian) has the ability and willingness to sign a written informed consent/assent.
2. Subject is of either gender and 12 to 40 years of age.
3. Subject is in good general health without clinically significant haematological, cardiac, respiratory, renal, endocrine, gastrointestinal, psychiatric, hepatic, or malignant disease, as determined by the investigator.
4. Subject has suitable venous access for blood sampling.
5. Subject is able and willing to complete the study and to comply with all study instructions and attend the necessary visits.
6. Subject has acne vulgaris of the face defined as:
 - a. 20 to 50 (inclusive) inflammatory lesions on the face
 - b. 20 to 100 (inclusive) non-inflammatory lesions on the face
 - c. An Investigator's Global Assessment (IGA) score for acne severity of 3 or 4 (moderate or severe) assessed on the face.
7. Subject has ≤ 2 nodular/cystic acne lesions (>5 mm in diameter).
8. Subject must refrain from the use of other treatments for acne during the study.
9. Subject must agree to not wash or shave their face, swim or otherwise get their face wet for at least 1 hour after application of study medication.
10. Subject must agree to maintain their regular use of sunscreens, moisturizers, shaving cream, and facial make up throughout the entire course of the study.
11. Male subjects and their partners must agree and commit to use a barrier method of contraception during the study and for 90 days after last study drug application.
12. A negative UPT result for all WOCBP at the Screening Visit and Baseline Visit, if applicable. A WOCBP is one who is not permanently sterilized or is not postmenopausal. Postmenopausal is defined as 24 months with no menses without an alternative medical cause.

13. Sexually active women must agree to use the following throughout the study and for 30 days after last study drug application:
 - a. One of these highly effective contraception methods
 - i. Intrauterine device (IUD); hormonal (injections, implants, transdermal patch, vaginal ring; tubal ligation; partner vasectomy, OR
 - b. Oral contraceptives WITH a barrier method (listed below), OR
 - c. Two barrier forms of contraception (listed below)
 - i. Male or female condom; diaphragm; cervical cap.

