9.4.3. Efficacy Analyses

The efficacy analyses will be performed using the ITT (primary) and PP (supportive) analysis sets. The efficacy variables include the IGA and lesion counts (inflammatory and non-inflammatory) collected at Screening/Baseline and the Day 14, Day 28, Day 56, and Day 84 Visits. Absolute and percent changes in lesion counts from Baseline will be calculated for each subject. The IGA will be dichotomized into "success" and "failure", with a subject considered a "success" at each individual visit if the IGA at that visit is Clear ("0") or Almost Clear ("1") and at least 2 grades less than the Baseline score. Efficacy variables also include the Acne-QoL assessed at Baseline and Day 84 which will be scored according to the author's scoring system (Martin 2001), and the subject's assessment of improvement (PRO) using proportions by category.

Descriptive statistics (including mean, median, standard deviation [SD], minimum, and maximum, unless otherwise stated) will be presented for the following parameters by study group using both the ITT and PP analysis sets:

- Inflammatory, non-inflammatory, and total lesion counts at Baseline and study Day 14, Day 28, Day 56, and Day 84,
- Absolute and percent change from Baseline in inflammatory, non-inflammatory, and total lesion counts at study Day 14, Day 28, Day 56, and Day 84, and
- IGA scores and frequency and percent distribution of the dichotomized IGA at study Day 14, Day 28, Day 56, and Day 84.

Primary endpoint:

The primary efficacy endpoint for the study is:

- Absolute change from Baseline in inflammatory lesion counts at Day 84.

Secondary endpoints:

The secondary endpoints for the study are:

- Absolute change from Baseline in non-inflammatory lesion count at Day 84,

- The percent change from Baseline in the inflammatory lesion count at Day 84,
- The percent change from Baseline in the non-inflammatory lesion count at Day 84,
- The proportion of subjects with at least a 2-grade reduction from the Baseline IGA score at Day 84,
- The proportion of subjects with an IGA score of “clear” or “almost clear” at Day 84, and
- The proportion of subjects with an IGA score of “clear” or “almost clear” at Day 84 and at least a 2-grade reduction from the Baseline IGA score.

Exploratory endpoints:

The exploratory endpoints are:

- The change from Baseline in the total lesion count at Day 84,
- The percent change from Baseline in the total lesion count at Day 84,

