- The change from baseline in the IGA scores and Day 84,
- The absolute and percent change from Baseline in inflammatory, non-inflammatory and total lesion counts at Day 14, Day 28 and Day 56.
- The proportion of subjects with at least a 2-grade reduction from the Baseline IGA score at Day 14, Day 28 and Day 56, and
- The proportion of subjects with an IGA score of “clear” or “almost clear” at Day 14, Day 28 and Day 56,
- The proportion of subjects with an IGA score of “clear” or “almost clear” at Day 14, Day 28 and Day 56 and at least a 2-grade reduction from the Baseline IGA score.
- The change from Baseline in the Acne-QoL at Day 84, and
- Subject’s assessment of the change in their acne from baseline to Day 84 (PRO).

Tests of superiority for the primary and secondary endpoints of absolute change from Baseline in lesion counts will be based on either parametric or nonparametric methods consistent with the statistical assumptions required to support the analyses. Specifically, the tests of superiority will be based on an ANCOVA with factors of treatment and the respective Baseline lesion count as covariates, or on ranked data submitted to an ANCOVA with factors of treatment, analysis center, and the respective Baseline lesion count as a covariate.

Data will be reviewed for skewedness (details in the SAP). If a parametric analysis is indicated, the results of the parametric analysis will be considered the primary analysis. If a nonparametric analysis is indicated, the absolute or percent changes in inflammatory lesion counts will be rank-transformed prior to submitting them to the ANCOVA. Results of the rank-transformed analyses

will then be considered the primary analysis; results of the nonrank-transformed analyses will be also presented.

The dichotomized IGA will be analyzed with logistic regression, adjusting for baseline IGA and site. Pairwise tests will be conducted comparing the treated groups to vehicle. The lesion count and IGA analyses employ the methods for handling missing data described in [Section 9.4.9](#).

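### SAP IGA models drop the protocol's baseline IGA (and, against 9.4.3, site), the ranked ANCOVA drops analysis center, and SAP Section 8 declares no changes

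*SAP*

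**What the plan says.** The protocol states the IGA model twice. The synopsis (Section 1) takes "Success on IGA defined as a score of clear or almost clear and/or at least a 2-grade improvement from Baseline" at Days 14, 28, 56 and 84 and says that it "will be analyzed using logistic regression, adjusting for Baseline IGA". Section 9.4.3 says: "The dichotomized IGA will be analyzed with logistic regression, adjusting for baseline IGA and site". The same section defines the dichotomized outcome as grade 0 or 1 "and at least 2 grades less than the Baseline score", that is, the composite only.

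For lesion counts the synopsis has a single model; the change "will be analyzed using ANCOVA with Baseline lesion count and treatment as covariates". Section 9.4.3 has two: a parametric ANCOVA with treatment and baseline count, and an alternative "on ranked data submitted to an ANCOVA with factors of treatment, analysis center, and the respective Baseline lesion count as a covariate". Analysis center is not defined anywhere.

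SAP 6.1.4 names baseline lesion count as the covariate for lesion endpoints and continues: "No other covariates are planned to be used in the analyses for this study". SAP 6.8.2.2 and 6.8.3.2 name no covariate for any IGA model, and the footnotes to Tables 14.2.2.3.1, 14.2.3.13.1, 14.2.3.14.1 and 14.2.3.15.1 list treatment group as the only factor. SAP 6.8.1 and footnote c of Table 14.2.1.1 give the ranked ANCOVA with treatment and baseline count only; this model becomes primary when the skewness test is significant at 0.01. SAP 4.1.2 stratifies randomization by site within the IWRS. SAP 6.1.7 says only that results from US and Australian sites will be pooled. SAP Section 8 declares no change in study conduct or planned analyses.

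**The concern.** Protocol 9.1 says that the protocol describes the statistical approaches and that the SAP adds detail on tables, listings and figures. Elsewhere the protocol hands specific items to the SAP: the per-protocol definition, the skewness details, and imputation and sensitivity analyses. Model terms are not among them. A SAP that removes terms and then states that nothing changed will produce a study report that misdescribes its own analyses.

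The terms are not arbitrary. A subject who enters as moderate needs two grades to reach almost clear and one who enters as severe needs three, so baseline IGA should predict composite success. Site is the stratification factor, yet no SAP efficacy model contains it. The ranked ANCOVA can become the primary analysis, so the missing center term can reach the primary endpoint. The protocol intends these tests to guide dose and sample size for Phase 3.

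**Working it through.** **Step 1. Terms side by side.** The plan gives no power calculation or effect figure here to reproduce, so the first check is textual.

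| Model | Protocol synopsis | Protocol 9.4.3 | SAP | SAP departs from |
|---|---|---|---|---|
| Composite IGA success | treatment, baseline IGA | treatment, baseline IGA, site | treatment | both on baseline IGA; 9.4.3 on site |
| Clear or almost clear | treatment, baseline IGA | no separate model | treatment | see Step 2 |
| At least 2-grade reduction | treatment, baseline IGA | no model stated | treatment | synopsis only |
| Parametric ANCOVA | treatment, baseline count | treatment, baseline count | treatment, baseline count | neither |
| Ranked ANCOVA | not described | treatment, center, baseline count | treatment, baseline count | 9.4.3 on center |

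The synopsis entries for the three IGA outcomes rest on its and/or wording.

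**Step 2. Which IGA outcomes differ.** Inclusion criterion 6c requires an IGA "score for acne severity of 3 or 4 (moderate or severe) assessed on the face". Let b be the baseline grade and f the Day 84 grade.
- b = 3: f ≤ 1 is equivalent to b − f ≥ 2, so all three outcomes coincide.
- b = 4: f ≤ 1 gives b − f ≥ 3, so clear/almost clear and the composite coincide. f = 2 gives b − f = 2, which counts only as a 2-grade reduction.

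For eligible subjects, then, clear/almost clear is the composite, and the 9.4.3 model applies to it in effect. The 2-grade reduction differs only by the severe-to-mild move. A subject randomized under a waiver or in error with b = 2 could reach f = 1 and be clear/almost clear without meeting the composite.

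**Step 3. Size, ranked ANCOVA.** The documents give no SD, site count, ICC or IGA rates, so every input below is an assumption. All runs use 360 subjects and two-sided 5% tests of one active arm against combined vehicle.

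*Unpooled center:* 15 sites of 24, blocks of 8, 4-lesion difference, residual SD 10, skewed errors, 2,000 runs. ICC = site variance / (site variance + 100).

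| Site SD | ICC | Power without → with center | Type I error without → with |
|---|---|---|---|
| 0 | 0 | 0.860 → 0.858 | 0.049 → 0.049 |
| 3 | 9/109 = 0.08 | 0.837 → 0.861 | 0.046 → 0.056 |
| 6 | 36/136 = 0.26 | 0.725 → 0.829 | 0.024 → 0.049 |

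*Pooled center:* SD 12, 5-lesion difference, 15 or 36 unequal sites pooled to at least 30 patients, blocks of 8 or 16, 2,500 runs per cell. Power gain from center, in points: ICC 0, −0.3 to +0.2; ICC 0.01, −0.1 to +0.2; ICC 0.05, 0 to +0.9; ICC 0.10, +0.8 to +1.8; ICC 0.20, +2.1 to +4.4.

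**Step 4. Size, IGA logistic model.**

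*Unpooled site:* 15 sites of 24, vehicle success 15% for a moderate subject at an average site, treatment OR 2.2, 20% severe, 1,000 runs. Power with treatment only / plus baseline IGA / plus baseline IGA and site:
- No site or baseline-IGA effect: 0.578 / 0.570 / 0.581.
- Site SD 0.5 logits, severe OR 0.5: 0.501 / 0.504 / 0.534.
- Site SD 1.0 logits, severe OR 0.3: 0.429 / 0.440 / 0.512.

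The Monte Carlo SE of a power near 0.5 is √(0.25/1000) = 0.016, so the first row shows no real difference.

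*Pooled center:* OR 2.5, vehicle success 20–25% in moderate and 5–10% in severe subjects, 10–30% severe, 4,000 runs per cell. Baseline IGA adds between 0.2 points (0.711 → 0.713) and 3.2 points (0.704 → 0.736). Pooled center adds a further 0.9 (0.667 → 0.676) to 1.9 (0.772 → 0.791) when site SD is 0.5 logits. Type I error is 4.0–5.3% with treatment only, 4.2–5.8% with baseline IGA and pooled center, and 5.1–6.6% with 36 unpooled sites.

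**The case against.** A SAP may refine a protocol, and here the protocol disagrees with itself: the synopsis has no site term. Protocol 9.2 says that secondary endpoints have no a priori hypotheses and leaves them to appropriate methods, and the IGA outcomes are secondary. Protocol 9.4.8 and SAP 6.1.8 call the tests exploratory. The SAP also tabulates composite success by baseline IGA and by region. On the assumed inputs, literal restoration of site with many small centers can push logistic type I error slightly above nominal, which treatment only does not do.

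Much of this stands as a limit on severity. It does not remove the mismatch. The synopsis and 9.4.3 agree on baseline IGA for the composite, so the protocol's inconsistency on site is no defense there. The tables by baseline IGA and region are descriptive and per-protocol only, so they do not replace adjustment. Freedom to choose a method does not make the statement in Section 8 true. Because 6.1.4 speaks of covariates while 6.8.1 separates factors from covariates, the omission of site and center rests on 6.8.1, 6.8.2.2, 6.8.3.2 and the table footnotes rather than on 6.1.4.

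Stronger readings are tempting and not supported:
- That the SAP contradicts both protocol statements for every IGA outcome. For the 2-grade reduction, 9.4.3 states no model, and the two-versus-three-grades argument does not carry over to it.
- That on center the SAP simply follows the synopsis. The synopsis describes no ranked ANCOVA to follow.
- That the planned primary analysis was altered outright. The parametric ANCOVA is unchanged; only the ranked alternative is affected.
- That leaving out the stratification factor inflates type I error. In these runs the models without it were near nominal or conservative.

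**Conclusion.** The mismatch is certain and textual. For the composite, and for clear/almost clear in eligible subjects, dropping baseline IGA departs from both protocol statements; for the 2-grade reduction it departs from the synopsis only. Dropping site from the composite model, and center from the ranked ANCOVA, departs from 9.4.3 only. Section 8 is therefore incorrect.

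The consequence is inaccurate reporting plus a modest loss of precision whose size is wholly conditional. If sites do not differ, center or site gains nothing real. Baseline IGA is worth at most about 3 power points on the inputs tried. Larger losses appear only under strong site effects: 0.829 − 0.725 = 10.4 points for the ranked test at an ICC of 0.26, and 0.512 − 0.429 = 8.3 points for the IGA model when site SD is 1.0 logits and the severe OR is 0.3. The documents neither support nor exclude such values. With exploratory tests, no type I error adjustment and a sample size not based on power, this should be fixed, but it does not invalidate the study.

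**What to change.** Before unblinding:

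1. Add baseline IGA to the logistic models in SAP 6.8.2.2 and 6.8.3.2 and to their table footnotes, and amend 6.1.4 to match.
2. Restore analysis center in the ranked ANCOVA (6.8.1 and its footnotes) and site in the composite IGA model, as in 9.4.3, and define center in 6.1.7. If many small sites make unpooled site effects unstable in the logistic model, set a pooling rule blind to treatment and declare it as a change. Reconcile the synopsis with 9.4.3 on site.
3. Correct Section 8 so that it lists and justifies every departure that remains.

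Adding center to the parametric ANCOVA, the repeated-measures model in 6.9 and the other IGA models is optional. It would stop the skewness test from also deciding which terms enter the model, but it is new design rather than a restoration.

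The cost is SAP wording, a few model lines and footnotes. Baseline IGA and site are already recorded. If sites do not differ, a pooled center term costs at most about 0.4% in the standard error of the parametric ANCOVA on the assumptions tried.

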6.1.5 Handling of Dropouts or Missing Data

All efforts will be made to minimize the occurrence of missing data. It is not expected that dropout rates will differ between groups. Therefore, the primary method of handling missing efficacy data in the ITT analysis set will be based on last observation carried forward (LOCF). Summary of efficacy and pharmacology variables for the PP subjects will be based on available data. No imputation will be done for non-efficacy related variables.

If a partial date is reported where the day is missing, then the day will be imputed as the first day of the month unless the month is the same month as the first application of study drug then the day will be that of first application with the month and year remaining the same. If a partial date is reported where the month is missing, then the month will be imputed to January unless the year is the same year as the first application of study drug then the month will be that of first application with the year remaining the same. If a partial date where both the day and month is missing, follow details as stated previously.

Missing AE start dates will be imputed using partial date imputation rules as previously described in this Section.

6.1.6 Interim Analyses and Data Monitoring

No interim analysis or data monitoring is planned for this study.

6.1.7 Multicenter Studies

This study will be conducted at multiple investigational sites in the United States and Australia with the intention of pooling the results for analysis.

6.1.8 Multiple Comparisons/Multiplicity

This Phase 2 study is designed to identify the response to two different concentrations and dosing frequencies of BTX 1503. Statistical tests applied to the outcomes will be exploratory for establishing the dose and sample size for Phase 3 studies. No adjustments for Type I error will occur.

6.1.9 Use of an Efficacy Subset of Subjects

Subjects randomized to study drug who complete the Day 84 visit without noteworthy study protocol violations, including compliance with study drug application, Day 84 visit window, and completion of efficacy evaluations on Day 84 will form the PP Population. The noteworthy

protocol violations will be defined at the time of evaluability evaluation, the time between the database soft lock and hard lock before unblinding.

Excluding subjects who have noteworthy protocol violations will decrease the variability in treatment response and will allow for a better determination of dose-response relationship of BTX 1503.

6.1.10 Active-Control Studies Intended to Show Equivalence

Not applicable to this study.

6.1.11 Examination of Subgroups

Subset analyses will be conducted for the PP analysis set on the primary efficacy endpoint and for the secondary endpoints, absolute change from Baseline in non-inflammatory lesion counts at Day 84 and subjects with an IGA score of “clear” or “almost clear” at Day 84 and at least a 2-grade reduction from the Baseline IGA score. These analyses will be summarized using descriptive statistics. The specific subsets within the PP analysis set that will be evaluated include:

- Baseline inflammatory lesion count (< median vs \geq median);
- Baseline non-inflammatory count (< median vs \geq median);
- Baseline total lesion count (< median vs \geq median and < 80th percentile vs \geq 80th percentile);
- Baseline IGA (3 (Moderate) vs 4 (Severe));
- Baseline Acne-QoL:
 - Self-Perception domain (< median vs \geq median),
 - Role-Social domain (< median vs \geq median),
 - Role-Emotional (< median vs \geq median), and
 - Acne Symptoms (< median vs \geq median);
- PRO (Improved (includes responses of much better and slightly better) vs. Same (includes response of the same) vs Worsened (includes responses of slightly worse and much worse));
- Geographical region (US vs AUS);

- Gender (Male vs Female);
- Ethnicity (Hispanic or Latino vs Non-Hispanic or Latino);
- Race (White vs Non-White); and
- Age (12 to <18 vs 18 to <30 vs 30 to 40).

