- Administration of the IGA by the PI or appropriately trained designee. The IGA will be graded based on the scale provided in [Table 2](#).

Table 2. Investigator’s Global Assessment Scale for Acne Vulgaris

| Grade | | Description |
|----------|--------------|----------------------------------------------------------------------------------------------------------------------------------------------------------------------------|
| 0 | Clear | No evidence of facial acne vulgaris |
| 1 | Almost Clear | Few non-inflammatory lesions (comedones) are present; a few non-inflamed papules (papules must be resolving and may be hyperpigmented, though not pink-red) may be present |
| 2 | Mild | Several to many non-inflammatory lesions (comedones) are present; a few inflammatory lesions (papules/pustules) are present; no nodulo-cystic lesions |
| 3 | Moderate | Many non-inflammatory (comedones) and inflammatory (papules/pustules) are present; there may or may not be one small nodulo-cystic lesion |
| 4 | Severe | Significant degree of inflammatory disease; papules/pustules are a predominant feature; a few nodulo-cystic lesions may be present; many comedones may be present. |

- Photographs of the subject’s face will be obtained at selected sites at the Baseline Visit and the Day 84 Visit. Details on the methods for photography are provided in the Photography Manual.
- At Baseline and at Day 84, the Acne-QoL will be administered.

- On Day 84, the subject will be asked to complete the Patient Reported Outcome (PRO) to assess the perception of their acne relative to their baseline. The subject will complete the assessment to answer the following question: “Compared to the beginning of treatment, my acne is?” with a response of “Much better”, “Slightly better”, “The same”, “Slightly Worse”, or “Much worse”.

For purposes of conducting IGA scoring, the following definitions will apply:

- Open comedo - a widely dilated follicle, plugged with sebum and keratin (blackhead)
- Closed comedo - a small, flesh-colored closed follicle, filled with sebum and firm to palpation
- Papule - a small solid, inflamed, elevated lesion less than 5 mm in diameter
- Pustule - a circumscribed, erythematous raised skin lesion containing white exudate or pus, less than 5 mm in diameter
- Nodule - an erythematous, raised, firm, deep-seated papule equal to or greater than 5 mm in diameter

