7.3.8. Schedule of Events Table – Subjects with Acne Vulgaris

The Schedule of Events is provided in [Table 3](#).

Table 3: Time and Events Schedule

| Parameter | Screening Visit (-35 to Day 1) | Baseline Visit (Day 1)^a | Day 14 Visit (Day 14 ±3 days) | Day 28 Visit (Day 28 ±5 days) | Day 56 Visit (Day 56 ±5 days) | Day 84 Visit^c (Day 84 ±5 days) |
|---------------------------------------------------|-------------------------------------------|----------------------------------------------------------------------------------|------------------------------------------|------------------------------------------|------------------------------------------|------------------------------------------------------|
| | Visit 1 | Visit 2 | Visit 3 | Visit 4 | Visit 5 | Visit 6 |
| Written informed consent/assent | X | | | | | |
| Medical history/ review of systems | X | | | | | |
| Demographics with Height and Weight | X | | | | | |
| Tobacco and Alcohol History | X | | | | | |
| Urine pregnancy test (WOCBP only) | X | X | | X | X | X |
| Eligibility criteria review | X | X | | | | |
| Safety Laboratory (CBC, chemistry and urinalysis) | | X | | | | X |
| Urine drug screening | X | X | | | | |
| Investigator's Global Assessment | X | X | X | X | X | X |
| Inflammatory and non-inflammatory lesion count | X | X | X | X | X | X |
| Photography of Face (selected sites) | | X | | | | X |
| Administer Acne-QoL | | X | | | | X |
| Administer PRO | | | | | | X |
| Ensure compliance with study drug administration | | | X | X | X | X |
| Study drug administration by site personnel (am) | | X | | | | |
| Study drug administration by subject | | Day 1 pm to Day 84 ^d ; Day 14, 28, 56, and 84 doses applied in clinic | | | | |
| Concomitant medications | X | X | X | X | X | X |
| Adverse events | | X | X | X | X | X |
| Cutaneous tolerability assessments ^b | | X | X | X | X | X |
| Dispense study drug and diary | | X | | X | X | |
| Collect diary and study drug | | | | X | X | X |

^a Screening and Baseline Visit may occur on the same day.

^b Assess cutaneous tolerability prior to and approximately 15 min after initial dose on Day 1 and the subject applications on Day 14, Day 28, Day 56, and Day 84

^c If subject discontinues treatment early, Day 84 evaluations will be performed when possible.

^d Subjects randomized to BID dosing will apply study drug in the morning and evening, 8 to 12 hours apart.

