5.1.1 Primary Efficacy Endpoint

The primary efficacy endpoint for the study is:

- Absolute change from Baseline in inflammatory lesion counts at Day 84.

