5.1.3 Exploratory Efficacy Endpoints

The exploratory efficacy endpoints are:

- The change from Baseline in the total lesion count at Day 84,
- The percent change from Baseline in the total lesion count at Day 84,
- The change from Baseline in the IGA scores at Day 84,
- The absolute and percent change from Baseline in inflammatory, non-inflammatory, and total lesion counts at Day 14, Day 28, and Day 56,
- The proportion of subjects with an IGA score of “clear” or “almost clear” at Day 14, Day 28, and Day 56,
- The proportion of subjects with at least a 2-grade reduction from the Baseline IGA score at Day 14, Day 28, and Day 56,
- The proportion of subjects with an IGA score of “clear” or “almost clear” at Day 14, Day 28, and Day 56 and at least a 2-grade reduction from the Baseline IGA score,
- The change from Baseline in the Acne-QoL at Day 84, and
- Subject’s assessment of the change in their acne from Baseline to Day 84 (Patient Reported Outcome [PRO]).

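### SAP 6.1.11 uses the Day 84 PRO, itself an efficacy outcome, as a subgroup factor, so the arm differences shown within PRO levels are not valid subgroup comparisons and are biased by an unknown amount

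*SAP*

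**What the plan says.** SAP 6.1.11 opens: "Subset analyses will be conducted for the PP analysis set on the primary efficacy endpoint". It adds non-inflammatory count change and IGA success, both at Day 84, and calls for descriptive statistics only. One entry in the list of subsets is "PRO (Improved (includes responses of much better and slightly better) vs. Same (includes response of the same", followed by a level for slightly or much worse.

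Protocol 7.1 fixes when the PRO is collected: "On Day 84, the subject will be asked to complete the Patient Reported Outcome (PRO". The question is "Compared to the beginning of treatment, my acne is", with five answers from much better to much worse. The events schedule in Protocol 7.3.8 marks it at the Day 84 visit alone: "Administer PRO | | | | | | X". SAP 5.1.3 lists the subject's "assessment of the change in their acne from Baseline to Day 84 (Patient Reported Outcome [PRO" as an exploratory efficacy endpoint. The primary endpoint in SAP 5.1.1 is "Absolute change from Baseline in inflammatory lesion counts at Day 84", measured at the same visit.

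The shells put all arms in adjacent columns within each PRO level: subgroup Table 14.2.1.3 pages 9 and 10 (the SAP uses that number twice; this is the PP subgroup table), Table 14.2.2.1.4 pages 9 and 10, and Table 14.2.2.3.3 page 9. They have the same title and layout as the pages for sex or region, and no footnote says that the PRO is an outcome.

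**The concern.** A subgroup table supports a treatment comparison when the subgroup was fixed before treatment began, because randomisation then balances the arms within it. Every other entry in the 6.1.11 list is a baseline measurement, a demographic factor or the region. The PRO is the subject's own verdict, at the end of treatment, on the disease that the endpoints count. If a dose clears lesions and subjects notice, some who would have answered Same on vehicle answer Improved on active. Improved on active and Improved on vehicle are then different kinds of subject, and more patients would not repair that.

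What is at stake is interpretation. SAP 6.1.8 says that the tests serve to set the Phase 3 dose and sample size, and SAP 6.1.9 presents the PP set as the better basis for judging dose response. Means by arm within PRO levels in that set invite a reading as effects in patients who did or did not improve, and such a reading could mislead the choice of dose.

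**Working it through.** The documents give no effect size, SD, PRO distribution or PRO-lesion correlation (SAP section 7 bases the sample size on clinical considerations), so there is no stated figure to reproduce. The size of the bias has to be shown over assumptions.

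**Assumed inputs.** True effect δ = 4 lesions (active minus vehicle, positive meaning a larger reduction); SD σ = 12; vehicle PRO split 60% Improved, 25% Same, 15% Worsened; correlation ρ between lesion reduction and a normal latent PRO score. The vehicle mean is set to 0, since only differences matter. The cut-points are the same in all arms: the vehicle 15th and 40th percentiles of the latent score, −1.036 and −0.253. A direct effect d of treatment on the latent score, in SD units, is 0 at first.

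**Formula.** The latent score has mean μ = ρm/σ + d and variance 1, where m is 0 on vehicle and δ on active (d applies to active only). For a level bounded by a and b,

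E(reduction | level) = m + σρ · [φ(a−μ) − φ(b−μ)] / [Φ(b−μ) − Φ(a−μ)].

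**One case in full: ρ = 0.6, Improved, d = 0.**
- Vehicle: μ = 0 and the share is 0.600. Mean = 12 × 0.6 × 0.3863 / 0.600 = 4.64.
- Active: μ = 0.6 × 4/12 = 0.2 and the share is 0.675. Mean = 4 + 12 × 0.6 × 0.3600 / 0.675 = 7.84.
- Difference = 7.84 − 4.64 = 3.20, which is 80% of the true 4. The Improved share has risen from 60% to 67.5%.

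**Treatment acts on the PRO only through lesions (d = 0).**

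| ρ | Improved | Same | Worsened | % of truth |
|---|---|---|---|---|
| 0 | 4.00 | 4.00 | 4.00 | 100 |
| 0.4 | 3.64 | 3.39 | 3.48 | 85–91 |
| 0.6 | 3.20 | 2.63 | 2.82 | 66–80 |
| 0.8 | 2.61 | 1.57 | 1.90 | 39–65 |

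Simulation with 2 million subjects per arm gives the same pattern. With δ/σ of 3/10 or 5/14, the difference weighted over levels is 94%, 83% and 67% of the truth at ρ = 0.3, 0.5 and 0.7. With vehicle splits of 40/40/20 or 75/17/8 and δ = 4, it is 3.7–3.8, 3.2–3.5 and 2.5–2.9 lesions at the same three correlations.

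**Treatment also acts on the PRO directly.**
- d = −0.3 (for example, active irritates more than vehicle), ρ = 0.6: 4.42, 4.68 and 4.58, so the effect is overstated by about 10 to 17%.
- d = +0.3, ρ = 0.5: 2.55, 1.34 and 1.68, so the shrinkage is stronger.
- d = +0.3, ρ = 0.5, no true lesion effect: −0.97, −1.71 and −1.48, so an inert dose looks worse than vehicle in every level.

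**Comparison without the split.** With d at any value, the arm difference that ignores the PRO stays at the true δ.

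These figures are for a lesion count treated as normal. The structural argument carries over to IGA success, but no size was calculated for it.

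**The case against.** **The direction is not known.** A reader might infer that a real effect necessarily shrinks in these tables. The documents do not support that. The PRO is a global question about the subject's acne, and Protocol 2.4.1 lists erythema, dryness, scaling and burning or stinging as risks, so treatment could affect the answer by a route other than lesion count. The calculation above shows the bias reversing in that case. This objection stands, and the claim has to be bias of uncertain sign and size. It does not rescue the display, because a bias that the tables cannot sign is no easier to read through.

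**The tables are descriptive.** The shells carry no p-values, LS means or interaction tests, and efficacy conclusions come from the ITT set (Protocol 9.3, SAP 6.1). A reader might infer that the primary result is compromised; it is not. The pages can also be read down a column, as lesion change by perceived improvement. But the layout offers the arm comparison, and a mean can mislead without a p-value.

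**Sampling error is larger.** At ρ = 0.6, if all 90 subjects per active arm and all 90 on combined vehicle entered the PP set, the expected cells (vehicle and active) are about 54 and 61, 22 and 20, and 14 and 10. The standard errors of the difference are about 2.0, 3.0 and 4.2 lesions, against shrinkage of 0.8, 1.4 and 1.2. This is correct, and it is a second reason not to compare arms within these cells. The bias adds to the noise.

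**The PP set is itself selected after randomisation.** It is, through completion, compliance and interfering medication (SAP 6.4.4). Removing PRO would not turn the remaining subgroup tables into randomised comparisons. The other factors in the list, however, do not sort subjects by the result of treatment.

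**Protocol 9.4.4 does not list PRO.** A reader might take this as further evidence of the flaw. It is not specific to PRO: the SAP also adds Acne-QoL and region, adds endpoints and moves from ITT to PP. That is a separate discrepancy.

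**Conclusion.** The concern holds in this form: the PRO is a Day 84 efficacy outcome rated at the same visit as the endpoints that it splits, and arm differences within its levels are not valid subgroup comparisons. That part rests on the documents alone, given only that treatment can influence the PRO.

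The size and direction rest on assumptions. If treatment reaches the PRO only through lesions, the within-level differences are roughly 65 to 90% of the truth at a correlation of 0.4 to 0.6 and 39 to 65% at 0.8, for an effect of 4 lesions, SD 12 and a 60/25/15 vehicle split. With no correlation there is no bias. With a direct treatment effect on the PRO, the differences can be too large, too small or of the wrong sign. The primary ITT ANCOVA and the secondary tests are unaffected. The point is worth correcting before the tables are produced, because the trial exists to choose a dose, but it does not threaten the trial's main conclusion.

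**What to change.** Delete PRO from the SAP 6.1.11 subset list, and remove the PRO pages from subgroup Table 14.2.1.3 (pages 9 and 10), Table 14.2.2.1.4 (pages 9 and 10) and Table 14.2.2.3.3 (page 9). PRO by arm, which is a proper randomised comparison in the ITT set, remains in Table 14.2.3.17.1, with its PP counterpart in 14.2.3.17.2.

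If the sponsor wants to know what lesion change subjects notice, add one table of lesion change by PRO category with all arms pooled, labelled as an association between two outcomes and not a treatment comparison.

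The cost is SAP wording and a few shells, with no change to data collection. The downside is that lesion change and IGA success by PRO level within each arm are no longer shown. If the sponsor insists on keeping those pages, the minimum is a footnote stating that the PRO is measured after treatment and that the columns must not be compared as treatment effects. That is weaker, because the misleading layout remains.
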